6.2.2. Continuous endpoints

Endpoints: ASDAS ESR and ASDAS CRP, BASDAI total and components, BASFI total and components, BAS-G total, SAGA, PGA, tender and swollen joint counts, dactylitis (total and number of affected digits) and enthesitis (MASES) scores, ESR, CRP, EQ-5D index and EQ-5D VAS, SF36 PCS and MCS, WPAI (4 derived subscales totals), SPARCC (SIJ and 6DVU).

- Analysis time points: All Period 1, 2 and 3 scheduled visits.
- Analysis population (method of imputation for missing data): FAS (LOCF and observed cases), where FAS populations are defined in each period in [Section 4.1](#).
- Analysis methodology: Change from baseline will be summarized using the methods specified in [Section 5.2.2](#).
- Supporting objective and Decision rule: Secondary Objectives.

Reporting results:

- Raw data: The sample size, mean, standard deviation, 95% CIs, minimum, maximum, median and 25th and 75th percentile values will be presented.
- Change from baseline: The sample size, mean, standard deviation, 95% CIs, minimum, maximum, median and 25th and 75th percentile values will be presented. Changes from period 1 baseline will be presented for all periods. For period 2 and 3, changes from the respective period baselines will also be presented.

6.3. Baseline and Other Summaries and Analyses

6.3.1. Baseline Summaries

Descriptive summaries of baseline demographic and disease characteristics will be provided. For binary/categorical characteristics sample size and the number and percent with each level will be and presented. For continuous characteristics the sample size, mean, standard deviation, 95% CIs, minimum, maximum, median and 25th and 75th percentile values will be presented.

6.3.2. Study Conduct and Subject Disposition

The number entering, completing and discontinuing from each treatment period will be tabulated for each treatment period. Discontinuations will be further summarized by reasons for discontinuation.

6.3.3. Concomitant Medications and Non-Drug Treatments

Prior and concomitant medications will be coded using the WHO Drug dictionary. The numbers of subjects using concomitant medications will be categorized by drug category and preferred term, and presented for each treatment group.

Concomitant medications and non-study treatments will be summarized separately for each period.

6.4. Subset Analyses

In addition to summarization of the overall population, the ASDAS flare endpoint will be summarized for key demographic and baseline disease characteristics for the B1801381 population. For each demographic and disease characteristic subgroup, the response in each subgroup category will be presented (responder count, group size, and response percent). In addition Cox regression models with factors for study, subgroup and study by subgroup interaction will be fit, separately for each subgroup. Results will be summarized with hazard ratios and 95% confidence intervals. The subgroups to be included are:

- Sex (Male, Female)
- Race (White, Non-White)
- Age category (<40 years, >=40 years)

- Weight (<70kg, ≥70 kg)
- Baseline hs-CRP status (High, Normal)
- HLA-B27 status (Positive, Negative)
- Concomitant use of DMARDs at Baseline (Yes, No)
- MRI sacroiliitis classification at Screening (Positive, Negative)
- Both positive MRI and elevated baseline hs-CRP (Yes/No)
- Baseline/screening MRI SIJ SPARCC score >2 (yes, no)
- History of IBD at Screening (Yes, No)
- History of uveitis at Screening (Yes, No)
- Disease duration <2 years (Yes, No).

Before the final model is determined, data patterns will be examined for feasibility issues, including highly correlated predictors and small cell size in subgroups. Adjustments will be made as necessary to address any such issues.

To support the interpretation of the primary analysis the following analysis will be performed:

- Sustained period one responders vs. responders at week 24 only.

An additional summary evaluating flare rates in those subjects who met the entry criteria only at week 24 and those who were sustained responders [subjects who, in addition to ASDAS ESR <1.3 at week 24, also have ASDAS ESR <1.3 at Week 12 or Week 16 (where ASDAS may not be greater than 2.1 at either time point)] will be provided. Populations and methodology will be applied as above.

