5.1. Hypotheses and Decision Rules

This study is an open-label study with one treatment group. Inferences will be based on point estimates and confidence intervals, rather than on hypothesis tests.

Except where stated, all confidence intervals will be 2-sided 95% confidence intervals.

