5.2.4. Analyses for Time to Event Data

Kaplan-Meier (KM) estimates, including plots, will be used to illustrate the time course of flare after treatment withdrawal. In addition to summarizing the data from the current study, the KM plots will show subjects from protocol B1801031 who met the entry requirements for the current trial withdrawal period. Those subjects did not have treatment withdrawn and will serve as a reference for evaluating the impact of treatment withdrawal. As a sensitivity analysis a life table approach will be used to compare the time to flare between the 2 studies, with time intervals based on visit windows.

In addition to the KM summaries, Cox proportional hazards models will be used to estimate the hazard ratio of continuing (B1801031) to withdrawn (B1801381) subjects.

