6. ANALYSES AND SUMMARIES

6.1. Primary Endpoint(s)

6.1.1. ASDAS flare

6.1.1.1. Primary Analysis

Endpoint: ASDAS flare (ASDAS ESR greater than or equal to 2.1).

- Analysis time points: Period 2 (over entire period).
- Analysis population: Period 2 FAS.
- method of imputation for missing data: LOCF.
- Primary analysis methodology: Descriptive summary only of proportion flared at each period 2 visit.

Reporting results:

- Descriptive: proportions (n/N) and 95% Confidence interval) at each period 2 visit.

- Supporting objective and Decision rule: Primary Objective.

Additional analyses for primary endpoint

- Method of imputation for missing data: None .
- Analysis methodology: Kaplan Meier estimate of time to flare and Cox proportional hazards model for evaluation of covariates and estimation of hazard compared to prior study B1801031 which had no withdrawal of treatment.
- Supporting objective and Decision rule: Primary Objective.
- Covariates used (Cox model): Covariates for the Cox regression model of time to flare will include, in addition to study (B1801031 vs B1801381), age, sex, geographic region, baseline CRP (normal vs. high), baseline MRI status (negative vs. Positive), disease duration, prior NSAID response (good vs. not) plus ASDAS values at weeks 12 and 24 or, in a separate model, sustained ASDAS inactive disease in period 1, defined as ASDAS ESR<1.3 at Week 12 or Week 16 (where ASDAS may not be greater than 2.1 at either time point) and at Week 24. Binary variables with small frequencies in either study will not be included in the Cox regression model.

Reporting results:

- Estimation:

Kaplan-Meier estimates of 25%, median and 75% survival and 95% confidence intervals.
Cox model based hazard ratio estimates for covariates and study.
- Tables: Present table with just HR and CI for “study” for 4 models:
 1. study only
 2. study plus baseline variables
 3. study plus baseline variables plus ASDAS continuous at 2 times
 4. study plus baseline variables plus sustained ASDAS remission
- Figures:

Kaplan Meir plots showing both studies flare events.

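### The SAP 6.4 subgroup Cox models contrast two non-randomised studies with no covariate beyond the subgroup factor; adding Week 24 ASDAS ESR would be a cheap safeguard

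*SAP*

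**What the plan says.** SAP 5.1 describes the trial plainly: "This study is an open-label study with one treatment group". The comparison with continued treatment comes from outside it. Of the B1801031 subjects, SAP 5.2.4 says: "Those subjects did not have treatment withdrawn and will serve as a reference for evaluating the impact of treatment withdrawal". Both SAP 5.2.4 and Protocol 9.2.2 limit that reference group to subjects who would have qualified for the withdrawal period, which under Protocol 4.2 means ASDAS CRP below 1.3 at Week 24.

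For the overall contrast, SAP 6.1.1.1 plans adjustment: "Covariates for the Cox regression model of time to flare will include, in addition to study (B1801031 vs B1801381), age, sex, geographic region", followed by CRP status, MRI status, length of disease and earlier NSAID response, and then "plus ASDAS values at weeks 12 and 24 or, in a separate model, sustained ASDAS inactive disease in period 1". The study hazard ratio is to be tabulated from four models. Model 1 has study alone, model 2 adds the baseline variables, model 3 is "study plus baseline variables plus ASDAS continuous at 2 times", and model 4 uses sustained remission in place of the ASDAS values.

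For the 13 subgroup variables, SAP 6.4 says: "In addition Cox regression models with factors for study, subgroup and study by subgroup interaction will be fit, separately for each subgroup". It continues: "Results will be summarized with hazard ratios and 95% confidence intervals". The only provision for changing these models is: "Before the final model is determined, data patterns will be examined for feasibility issues, including highly correlated predictors and small cell size in subgroups".

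**The concern.** In these models the study term stands for withdrawal against continuation, but it also stands for every other difference between the two study populations. The SAP recognises this for the overall hazard ratio and adds covariates in steps. It does not carry any of them into 6.4, except where a subgroup factor is itself one of them (sex, age, CRP, MRI, disease duration). The feasibility sentence deals with collinearity and thin cells, not with confounding.

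Flare is an absolute cut on ASDAS ESR (2.1 or more), so a subject who starts closer to the cut needs less change to reach it. If the two studies differ in starting ASDAS ESR, each subgroup hazard ratio absorbs part of that difference. If they differ more in one subgroup level than in the other, the interaction term can suggest that withdrawal matters more in one kind of patient when it does not.

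**Working it through.** **Plan's own figures.** The documents state no power or precision for the between-study or subgroup models. The only sizing figures are the half-widths in Protocol 9.1, and both reproduce. For flare, 1.96 × √(0.70 × 0.30 / 96) = 9.2%, against about 10% stated. For retreatment, with 0.70 × 96 ≈ 67 subjects, 1.96 × √(0.60 × 0.40 / 67) = 11.7%, against about 12% stated.

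**Does the entry rule equalise the starting point?** Use the SAP 3.1 formulas with all four symptom items at 1 cm and CRP at or below 2 mg/L (set to 2).
- ASDAS CRP = 0.121 + 0.110 + 0.073 + 0.058 + 0.579 × ln 3 = 0.362 + 0.636 = 1.00, so the subject qualifies.
- ASDAS ESR = 0.08 + 0.11 + 0.09 + 0.07 + 0.29 × √ESR = 0.35 + 0.29 × √ESR. This gives 1.27 at ESR 10, 1.65 at ESR 20 and 2.18 at ESR 40.

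One qualifying ASDAS CRP value is thus compatible with starting ASDAS ESR values about 0.9 apart, the highest already above the flare cut. The ESR 40 case is constructed to show the gap and is not offered as typical. On the CRP scale the restriction is tight: the floor is 0.579 × ln 3 = 0.64, so entrants lie in a band of 0.66, with an SD of at most 0.33. The ESR scale has no such limit.

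**How large could a false interaction be?** All inputs on B1801031 are assumptions:
- 96 withdrawn subjects with 70% flare by 40 weeks (Protocol 9.1), and 60 reference subjects (assumed).
- True hazard ratio, withdrawn to continuing, of 4 in both subgroup levels; no true interaction.
- Week 24 ASDAS with SD 0.4; flare hazard multiplied by g = 2 or 4 per unit.
- A between-study difference d = 0.2 or 0.4 in one subgroup level only.

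Exponential flare times were censored at 40 weeks and fitted by Cox models, 400 runs per setting. As a rough guide, the expected false ratio is g^d.

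| g | d | g^d | Planned model | With Week 24 ASDAS |
|---|---|---|---|---|
| 2 | 0.2 | 1.15 | 1.10 | 0.96 |
| 2 | 0.4 | 1.32 | 1.28 | 0.98 |
| 4 | 0.2 | 1.32 | 1.25 | 0.99 |
| 4 | 0.4 | 1.74 | 1.64 | 1.01 |

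Repeat runs gave 1.09 to 1.11 at the smallest setting, 1.59 to 1.60 at the largest, and 0.94 to 1.00 after adjustment. Unadjusted 95% coverage was 93% to 95% in the first three settings and 84% to 90% in the last; adjusted coverage was 95% to 97%. With d = 0.1 the false ratio was 1.04 to 1.14 and coverage 94% to 97%. The mean standard error was 0.564 unadjusted and 0.575 adjusted (0.575 / 0.564 = 1.02). SAP 5.2.4 defines the hazard ratio the other way round (continuing to withdrawn), so these ratios would appear inverted.

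**When does the interaction escape?** A second simulation used 20,000 subjects per run and a binary prognostic factor with hazard ratio 2 or 3.
- Same imbalance in both levels (60% against 40%): the interaction stayed at 1.01 and 0.99, but the subgroup hazard ratios were 4.2 to 4.3 unadjusted, against 3.9 to 4.0 adjusted.
- Imbalance in one level only (70% against 30%): the interaction was 1.28 and 1.49 unadjusted, against 0.96 and 0.95 adjusted.

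**The case against.** Several points on the other side stand.

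A reader might infer that the subgroup hazard ratios have no overall figure to sit beside. That is not so. Model 1 of SAP 6.1.1.1 is also unadjusted and is reported, so it is a like-for-like comparator, and models 2 to 4 show how far covariates move the overall result. What is missing is a subgroup result that can be read beside models 2 to 4.

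The entry restriction is real protection. The simulated SD of 0.4 could not even occur on the ASDAS CRP scale, so these settings make sense only for ASDAS ESR. Placing all the imbalance in one subgroup level is also the layout that most favours the concern.

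The bias is modest against the noise. With a standard error of 0.564, the interaction interval runs from about one third to three times the estimate (exp(1.96 × 0.564) = 3.0). In three of the four settings the bias is under half a standard error (ln 1.28 / 0.564 = 0.44).

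It is also tempting to ask for every 6.1.1.1 covariate in every subgroup model. Only one covariate was simulated, and the events may not support more. On the same inputs the withdrawn cumulative hazard is −ln 0.30 = 1.20, the reference value is 1.20 / 4 = 0.30, and 60 × (1 − e^−0.30) ≈ 16 reference flares, about 8 per level in an even split.

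Finally, SAP 5.1 and 5.2 frame the work as estimation, and no interaction test or decision rule is attached to the subgroups.

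**Conclusion.** The concern holds in a limited form. The 6.4 models make a non-randomised contrast with no covariate beyond the subgroup factor, while 6.1.1.1 adjusts the same contrast. The ASDAS CRP entry rule narrows but does not remove differences in starting ASDAS ESR. Subgroup hazard ratios can carry such differences. The interaction is biased only where the imbalance, or its prognostic effect, differs between subgroup levels.

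On the stated assumptions the false interaction ratio is about 1.1 to 1.6, and interval coverage suffers materially only at the most extreme setting. The documents give no B1801031 sample size, entry data or flare rate, so they do not support saying that the planned subgroup results will be biased, in which direction, or by how much. Nor do they support reading this as a threat to the primary result: the flare proportion is a single-arm estimate and does not use these models. This is a change to consider for a descriptive, supportive analysis.

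**What to change.** In SAP 6.4, add Week 24 ASDAS ESR as a covariate in each study-by-subgroup Cox model, and report the adjusted hazard ratios and interaction beside the unadjusted ones. Name the ESR version explicitly, because SAP 6.1.1.1 does not say which ASDAS its Week 12 and Week 24 covariates use. Add further 6.1.1.1 baseline covariates, other than the subgroup factor itself, only where the number of flares in both studies supports them.

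The cost is a sentence of SAP wording and one more model term. Week 24 ASDAS is already called for in 6.1.1.1, and ASDAS ESR is already the scale for flare. The standard error rises by about 1% to 2% for this one covariate; that figure should not be carried over to a larger set. No sample size or stated precision changes.

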3. ENDPOINTS AND BASELINE VARIABLES: DEFINITIONS AND CONVENTIONS

3.1. Primary Endpoint(s)

The primary endpoint for this study is occurrence of flare within 40 weeks (defined as an ASDAS ESR greater than or equal to 2.1) following withdrawal of ETN. The key secondary endpoint is the time to flare after withdrawal of ETN.

ASDAS is calculated from the following parameters:

1. Total back pain (BASDAI question 2) (units CM, range 0-10).
2. Subject global assessment of disease activity (units CM, range 0-10).
3. Peripheral pain/swelling (BASDAI question 3) (units CM, range 0-10).
4. Duration of morning stiffness (BASDAI question 6) (units CM, range 0-10).
5. C-reactive protein (CRP) in mg/litre or ESR in mm/h.

The ASDAS score is then calculated as follows:

$ASDAS\ ESR = (0.08 \times \text{total back pain}) + (0.11 \times \text{subject global}) + (0.09 \times \text{peripheral pain/swelling}) + (0.07 \times \text{duration of morning stiffness}) + (0.29 \times \sqrt{ESR})$.

$ASDAS\ CRP = (0.121 \times \text{total back pain}) + (0.110 \times \text{subject global}) + (0.073 \times \text{peripheral pain/swelling}) + (0.058 \times \text{duration of morning stiffness}) + (0.579 \times \ln(CRP+1))$.

Note: for ASDAS CRP, hsCRP observed values of <2 mg/L will be converted to the value of 2 in the calculation of ASDAS CRP. Also, for values ≥ 2 mg/L that are below the limit of detection (conventional CRP), as indicated by “<” in the field (eg, <4.1), a value of 2 should be used in the calculation of ASDAS CRP.

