Appendix 2. STATISTICAL METHODOLOGY DETAILS

Appendix 2.1. Flare using ASDAS CRP

Subjects will be entered into the retreatment period based on occurrence of flare, defined as an ASDAS ESR value ≥ 2.1 during the withdrawal period. A secondary set of efficacy endpoint analyses for the retreatment period will include only those subjects who also had an ASDAS CRP value ≥ 2.1 .

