Appendix 2.2. Sustained Remission

For the withdrawal and retreatment periods, sensitivity analyses for the relapse, ASDAS inactive disease and ASAS40 endpoints by period 1 sustained inactive disease status (sustained or not, as defined under “Covariates”) will be provided. Tables presenting these endpoints by period 1 inactive disease status (Yes/No) will be provided.

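### SAP 6.1.1.1, 6.4 and Appendix 2.2 classify Period 1 sustained inactive disease by ASDAS ESR, while Period 2 entry and inactive disease itself are set on ASDAS CRP, so some entrants can be misclassified relative to the index on which they entered

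*SAP*

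**What the plan says.** Period 2 entry requires ASDAS CRP below 1.3 at Week 24 (Protocol 4.2; SAP 2.2.1). SAP 2.1.1 and 3.2 attach the term inactive disease to the same index and cut-off. Flare is on the other index: ASDAS ESR of 2.1 or more (Protocol 2.2.1; SAP 3.1).

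The Period 1 sustained class is also on the ESR index:

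- SAP 6.1.1.1 lists as a Cox covariate "sustained ASDAS inactive disease in period 1, defined as ASDAS ESR<1.3 at Week 12 or Week 16", with the same cut-off required at Week 24 and no value above 2.1 at Week 12 or Week 16. It enters the fourth reported model, "study plus baseline variables plus sustained ASDAS remission".
- SAP 6.4 defines sustained responders as subjects who, "in addition to ASDAS ESR <1.3 at week 24, also have ASDAS ESR <1.3 at Week 12 or Week 16", with the same 2.1 condition. It sets their flare rate against that of "those subjects who met the entry criteria only at week 24".
- Appendix 2.2 applies the covariate definition to "sensitivity analyses for the relapse, ASDAS inactive disease and ASAS40 endpoints by period 1 sustained inactive disease status", and adds: "Tables presenting these endpoints by period 1 inactive disease status (Yes/No) will be provided".

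The 2.1 condition refers only to ASDAS and does not name the index. No reason is given for moving from CRP to ESR. For retreatment, by contrast, the SAP does deal with the two indices. Appendix 2.1 keeps the ESR definition of flare and adds a CRP check: "A secondary set of efficacy endpoint analyses for the retreatment period will include only those subjects who also had an ASDAS CRP value" of 2.1 or more.

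**The concern.** The 6.4 summary is offered to help interpret the primary flare proportion, by separating subjects whose response had lasted from those who had only just qualified. Its Week 24 condition reads as if it restated the entry criterion. It does not, because entry was on CRP. A subject who is inactive at Week 24 by the SAP's own definition can fail the Week 24 leg of sustained inactive disease. A subject who first reached the entry threshold at Week 24 can count as sustained.

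Appendix 2.2 adds a labelling problem. It would tabulate the inactive-disease endpoint, which is defined on CRP, by an inactive-disease status defined on ESR, with nothing to tell the reader that the two differ.

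What is at stake is whether these tables show the contrast they describe.

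**Working it through.** No sample size or precision figure in the plan depends on this definition, so there is no stated figure to reproduce. The check is whether the two indices can disagree at the 1.3 cut-off, and at what values.

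**Inputs** (Protocol 9.2.1; SAP 3.1). Items are on a 0–10 cm scale: B back pain, G subject global, P peripheral pain/swelling, M duration of morning stiffness.

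- ASDAS CRP = 0.121B + 0.110G + 0.073P + 0.058M + 0.579 ln(CRP + 1)
- ASDAS ESR = 0.08B + 0.11G + 0.09P + 0.07M + 0.29√ESR
- The SAP adds a floor: "hsCRP observed values of <2 mg/L will be converted to the value of 2 in the calculation of ASDAS CRP". The smallest possible CRP term is therefore 0.579 × ln 3 = 0.636.

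With all four items equal to s cm, the item sums are 0.362s (CRP version) and 0.35s (ESR version).

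**Subject 1: inactive throughout by the entry index, coded not sustained.** s = 1, hsCRP at or below 2 mg/L and ESR 12 mm/h at Weeks 12, 16 and 24.

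- ASDAS CRP = 0.362 + 0.636 = 0.998 at each visit.
- ASDAS ESR = 0.35 + 0.29√12 = 0.35 + 1.005 = 1.355 at each visit.

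**Subject 2: first meets the entry threshold at Week 24, coded sustained.** s = 1 and ESR 6 mm/h throughout; hsCRP 5 mg/L at Weeks 12 and 16, then at or below 2 mg/L at Week 24.

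- ASDAS CRP at Weeks 12 and 16 = 0.362 + 0.579 × ln 6 = 0.362 + 1.037 = 1.399; at Week 24, 0.998.
- ASDAS ESR = 0.35 + 0.29√6 = 0.35 + 0.710 = 1.060 at each visit.

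**ESR at which a low-CRP entrant stops counting as inactive.** Setting ASDAS ESR to 1.3 gives ESR = ((1.3 − 0.35s)/0.29)². With hsCRP at or below 2 mg/L:

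| s (cm) | ASDAS CRP | ESR at which ASDAS ESR = 1.3 (mm/h) |
|---|---|---|
| 0 | 0.636 | 20.1 |
| 1 | 0.998 | 10.7 |
| 1.5 | 1.179 | 7.1 |
| 1.8 | 1.288 | 5.3 |

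**Does this depend on equal items?** The ratio of the ESR weight to the CRP weight is 0.661 for B, 1.000 for G, 1.233 for P and 1.207 for M. Holding the CRP item sum at 0.362, the ESR item sum lies between 0.239 (back pain only, 0.362/0.121 = 2.99 cm) and 0.446 (peripheral only, 0.362/0.073 = 4.96 cm).

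- Subject 1 pattern: the ESR at which ASDAS ESR reaches 1.3 lies between ((1.3 − 0.446)/0.29)² = 8.7 and ((1.3 − 0.239)/0.29)² = 13.4 mm/h.
- Subject 2 pattern: ASDAS ESR lies between 0.239 + 0.710 = 0.95 and 0.446 + 0.710 = 1.16, so it is below 1.3 for every item mix.

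**Does using ASDAS CRP alone settle the groups?** Not quite. Take items at 0.5 cm at Weeks 12 and 24 and 5 cm at Week 16, with hsCRP at the floor. ASDAS CRP is 0.181 + 0.636 = 0.817, then 1.810 + 0.636 = 2.446, then 0.817. This subject is below 1.3 at Week 12 but is excluded from the sustained class by the 2.1 condition at Week 16. The comparison group therefore has to be named whichever index is used.

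**The case against.** The best case for the plan is that the ESR index may be deliberate. Flare is on ASDAS ESR, so a prior-response covariate on the same index is coherent, and a programmer would not be in doubt about the rule in 6.1.1.1. This stands for Cox model 4, where the point reduces to labelling. It carries less weight for 6.4 and Appendix 2.2, which describe subjects by inactive-disease status, a term the SAP otherwise ties to CRP.

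A second argument is that model 3 already adjusts for ASDAS values at Weeks 12 and 24, giving a look at earlier response that does not use the sustained class. That is true, although the index for those values is not named, and it does not help the 6.4 or Appendix 2.2 tables.

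A reader might go further and infer that the two 6.4 groups fail to divide the entrants. If the comparison group is taken to be those below the CRP cut-off at Week 24 and at neither Week 12 nor Week 16, Subject 1 falls in neither group and Subject 2 in both. The documents do not support resting the point on that. The Period 2 criteria in Protocol 4.2 are completion of Period 1 and a Week 24 value, so they cannot be met at Week 12 or 16. The heading of the 6.4 item, the sustained-or-not wording of Appendix 2.2 and the Y/N description in SAP Table 1 all point to a two-way split. The 6.4 phrase is loose and is best read as all other entrants. Both subjects then have a group; what remains is that each is misclassified relative to the entry index.

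**Conclusion.** The mismatch of index is in the text, and it can misclassify entrants in both directions at modest symptom and marker values. The result rests only on the two formulas, the hsCRP floor and the stated cut-offs. The worked subjects are illustrations, and the bounds show that they do not hinge on equal item scores.

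The effect is confined to the 6.4 sustained-responder summary, Cox model 4 and the Appendix 2.2 tables. Eligibility, the primary flare proportion, the Kaplan-Meier estimates and Cox models 1 to 3 do not use the sustained class. A reader should not infer that the primary result is in doubt, or that ESR is the wrong index for the covariate.

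The number of discordant subjects among the roughly 96 expected entrants cannot be derived from the documents, because it depends on the joint distribution of ESR, hsCRP and symptoms in responders. The calculation shows that discordance is possible, not that it is common. This is a minor correction.

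**What to change.** - In the 6.4 summary and the Appendix 2.2 tables, report sustained status on the entry index (ASDAS CRP below 1.3 at Week 24 and at Week 12 or Week 16) alongside the present ASDAS ESR version. Label each with its index. This follows the approach Appendix 2.1 already takes for retreatment.
- Name the index for the 2.1 condition, and use the same one as in the rest of each definition.
- State in 6.4 that the comparison group is all other Period 2 entrants.
- In Cox model 4, the ESR covariate may stay if it is labelled as ASDAS ESR. Add a CRP version only if B1801031 has hsCRP at the visits concerned. The same condition applies to any two-study Cox fit of this contrast under 6.4.

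The cost is wording in SAP 6.1.1.1, 6.4 and Appendix 2.2, and one rerun of the affected tables. Protocol 6.3 collects hsCRP and ESR at every Period 1 visit, so this trial needs no new data. Selecting the B1801031 reference subjects under SAP 5.2.4 already requires ASDAS CRP at their qualifying visit, but that study's hsCRP schedule at Weeks 12 and 16 is not in the documents and must be checked first.
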